## **Statistical Analysis**

Intention-to-treat (primary analysis) and per protocol analyses will be performed. Chi-squared and Fisher's exact tests will be used to compare categorical variables as appropriate. Continuous variables will initially be assessed for distribution pattern via the Kolmogorov-Smirnov test. Normally distributed variables will be compared using Student's t-tests and non-normally distributed variables will be analyzed with the Mann-Whitney U test. These analyses will be supplemented by multivariable logistic regressions to adjust for confounders.

Tests with  $p < 0.05$  will be considered statistically significant. Analyses will be performed using Stata (Stata Corp., College Station, TX).

For the primary outcome of lactate, 95% confidence intervals (CI) will be calculated for the mean cord lactate levels in each group. Comparison of the 95% CI in each group will then determine non-inferiority or inferiority.

Additional interaction analyses for the primary outcome will be performed for the following subgroups:

- 1) Presence of chronic medical conditions (hypertensive disorder, diabetes)

- a. Patients with hypertensive disorders (chronic hypertension, gestational hypertension, preeclampsia)
- b. Patients with diabetes mellitus (gestational diabetes, T1DM, T2DM)
- 2) Recurrent late decelerations pre intervention
- 3) Recurrent variable decelerations pre intervention
- 4) Prolonged deceleration pre intervention
- 5) Fetal tachycardia pre intervention
- 6) Fetuses with intrauterine growth restriction
- 7) Chorioamnionitis
- 8) Within oxygen group: Duration of oxygen exposure
  - a. <50% of total duration of active labor (onset of active labor to delivery)
  - b. >50% of total duration of active labor (onset of active labor to delivery)

Odds ratios and 95% CI will be calculated for the secondary outcome of persistent Category II FHT. Kaplan-Meir analyses will be performed for fetal monitoring analyses.

For the outcome of maternal and cord blood MDA, a fetal MDA will be calculated by subtracting umbilical artery MDA from maternal MDA for each sample. The calculated mean fetal MDA and maternal MDA values will then be compared between groups using either Student t test or Mann Whitney U test.

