### **Sample size analysis**

A review of previously collected data from our institution of 5182 term singleton pregnancies revealed a mean cord lactate of  $3.5 \pm 1.6$  mmol/L in women with Category II FHT within 30 minutes of delivery. All of these deliveries were managed using our current protocol of routine oxygen administration for Category II FHT. Given the normal mean lactate seen in our population of patients with Category II FHT, a noninferiority approach was selected to test our hypothesis that room air is not inferior to oxygen administration in treating Category II FHT. A total sample size of 98 patients will be needed to detect a non-inferiority margin of 30% with 90% power, using a one-sided two-sample t-test (alpha 0.025). To accommodate a 15% drop out/cross over rate, a total of 114 patients will be needed. We plan on performing an initial compliance run-in of 6 patients making the total enrollment 120 patients. Data analysis will only be performed on the 114 patients enrolled after the initial 6 patients enrolled/randomized in the compliance run-in/pilot. Previous studies have shown an increased risk for neonatal morbidity with cord lactate cut-offs ranging from 3.2-6.0. The margin of noninferiority was

therefore set at a lactate cut-off of 4.5, above which there is a clear association with neonatal morbidity.

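### The plan does not say which between-arm test applies to lactate: a normality pre-test can select Mann-Whitney, whose ordinary p-value does not address the non-inferiority margin

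*Combined protocol and SAP*

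**What the plan says.** Three statements in the combined protocol and SAP bear on how lactate is compared between arms.

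- **General rule (Statistical Analysis).** "Continuous variables will initially be assessed for distribution pattern via the Kolmogorov-Smirnov test". Then: "Normally distributed variables will be compared using Student's t-tests and non-normally distributed variables will be analyzed with the Mann-Whitney U test". No variable is exempted. The section does not give the level of the pre-test, whether it is run on pooled data or by arm, or whether it is corrected for an estimated mean and SD.
- **Lactate rule (same section, later paragraph).** "For the primary outcome of lactate, 95% confidence intervals (CI) will be calculated for the mean cord lactate levels in each group". Then: "Comparison of the 95% CI in each group will then determine non-inferiority or inferiority". No normality condition is attached.
- **Sizing (Sample size analysis).** "A total sample size of 98 patients will be needed to detect a non-inferiority margin of 30% with 90% power". The planning values are a mean of 3.5 and an SD of 1.6 mmol/L, and the test assumed is a two-sample t-test, one-sided at 0.025. The margin is also described as "therefore set at a lactate cut-off of 4.5, above which there is a clear association with neonatal morbidity".

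Nothing states whether the lactate rule replaces the general rule or is added to it.

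**The concern.** Lactate is continuous, so the general rule covers it as written. Its only between-arm tests for a continuous outcome are the two that the pre-test chooses between. The lactate paragraph gives an interval for each arm but no interval or test for the difference, and it does not mention the margin. An analyst who found lactate non-normal could report a Mann-Whitney p-value as the between-arm result and be following the plan.

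That p-value answers a different question from the one that sized the trial. The margin is on the mean, in mmol/L. An ordinary Mann-Whitney test compares the two distributions with no margin, so a non-significant result is not evidence of non-inferiority. The hypotheses in the Specific Aims and Strategy sections are worded as an absence of difference, which makes that misreading easy. The pre-test's own details are open too, and they strongly affect which test is used.

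**Working it through.** **Inputs.** Mean 3.5, SD 1.6, margin 30%, one-sided alpha 0.025, power 90% and total 98 (114 after drop-out and crossover) come from the Sample size analysis. The 1:1 allocation comes from the Strategy section. The shape of the lactate distribution is not given. Normal, gamma and lognormal shapes with mean 3.5 and SD 1.6 are therefore assumptions, used to show a range.

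**Step 1: the plan's sample size.** Margin = 0.30 × 3.5 = 1.05 mmol/L.

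n per arm = 2 × (1.960 + 1.282)² × 1.6² / 1.05² = 2 × 10.51 × 2.56 / 1.1025 = 48.8, so 49 per arm and 98 in total. This reproduces the stated figure. The t-distribution version gives 49.8, so 50 per arm. The trial was therefore sized for a difference in means.

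**Step 2: how often the pre-test would call lactate non-normal** (5% level, pooled sample, 2,000 simulated trials). Gamma shape parameter = (3.5/1.6)² = 4.79. Lognormal log-variance = ln(1 + (1.6/3.5)²) = 0.190.

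| Assumed shape | n | Uncorrected KS | Lilliefors-corrected KS |
|---|---|---|---|
| Normal | 98 | 0% | 4% |
| Normal | 114 | 0% | 4% |
| Gamma | 98 | 6% | 61% |
| Gamma | 114 | 7% | 64% |
| Lognormal | 98 | 25% | 87% |
| Lognormal | 114 | 34% | 90% |

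The plan names Kolmogorov-Smirnov without a correction, so the uncorrected column is the closer reading. The gap between the columns shows how much rests on an unstated choice.

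**Step 3: what an ordinary Mann-Whitney p-value says at the margin.** With 49 per arm and 10,000 simulated trials, the true mean excess on room air was set to 1.05. It was added either as a shift or as a multiple (3.5 × 1.3 = 4.55, and 4.55 − 3.5 = 1.05). At this point a valid one-sided test should conclude non-inferiority in 2.5% of trials.

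| Shape | Effect | Two-sided Mann-Whitney p ≥ 0.05 | t-test against the margin: concludes non-inferiority | Mann-Whitney shifted by the margin: concludes non-inferiority |
|---|---|---|---|---|
| Normal | shift | 12% | 0.026 | 0.026 |
| Normal | multiple | 23% | 0.024 | 0.025 |
| Gamma | shift | 8% | 0.026 | 0.027 |
| Gamma | multiple | 24% | 0.029 | 0.051 |
| Lognormal | shift | 4% | 0.024 | 0.021 |
| Lognormal | multiple | 17% | 0.028 | 0.061 |

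If non-significance were read as support for room air, it would give that support in about 4% to 24% of trials in which room air is worse by the full margin.

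**Step 4: the t-test fixed in advance.** With truly equal arms, simulated power of the t-test against the margin is 0.90 (normal), 0.90 (gamma) and 0.89 (lognormal). Its type I error is the fourth column above, 0.024 to 0.029. These runs used the pooled-variance test. With equal arm sizes the Welch statistic is the same number and only the degrees of freedom differ.

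**The case against.** The strongest reply is that lactate has its own rule. The lactate paragraph ties the non-inferiority conclusion to intervals for means with no normality condition, the trial is sized on a t-test, and a specific rule ordinarily governs a general one. This stands. A reader might infer that the non-inferiority decision itself depends on the pre-test, or that a failed pre-test would leave only a non-significant result to report. The documents do not support either inference: the per-arm mean intervals are to be calculated whatever the distribution. What the reply does not settle is which between-arm test accompanies them, because the plan never says that the general rule is set aside.

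Other limits also stand:

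- A reader might take 3.5 ± 1.6 as proof of skew. Mean minus 2 SD is 3.5 − 3.2 = 0.3, which is still positive, so a roughly symmetric distribution is also possible.
- A rank test is not wholly unable to use a margin. Shifted by the margin, it holds its level under a pure shift (0.021 to 0.027). It tests the mean difference only if the arms have the same shape, and under a multiplicative effect its error reaches 0.051 (gamma) or 0.061 (lognormal). The plan does not specify such a test.
- Non-significance at an excess inside the margin, such as 0.7 mmol/L, would not show harm, since room air is non-inferior there. An ordinary t-test is also often non-significant in that case. The fault is the missing margin, not ranks as such.
- Pre-testing for secondary outcomes without a margin is a common convention.

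**Conclusion.** The point holds as an ambiguity in the analysis of the primary outcome. The general rule may let the data choose the between-arm test of lactate, and one branch gives a p-value that does not test the margin. At a true excess of 1.05 mmol/L and 49 per arm, that p-value is non-significant in about 4% to 24% of trials, depending on shape and on whether the effect is a shift or a multiple. The chance of reaching that branch at n = 114 is about 0%, 7% or 34% for normal, gamma or lognormal lactate with the uncorrected pre-test. All these rates rest on assumed shapes and should be read as a range. The ambiguity itself comes from the text and needs no assumption about skew.

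**What to change.** State in the Statistical Analysis section that lactate is exempt from the Kolmogorov-Smirnov rule. Whatever its distribution, analyse it by the two-sided 95% confidence interval for the difference in means (room air minus oxygen), from a Welch t-test or a linear model. Non-inferiority is concluded if the upper limit lies below one pre-stated margin. Label any rank or bootstrap analysis of lactate as sensitivity only.

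The single margin has to be chosen explicitly. Thirty per cent of 3.5 is 1.05, whereas the 4.5 cut-off implies 4.5 − 3.5 = 1.0. With 1.05, N stays at 98. With 1.0, the formula in Step 1 gives 2 × 10.51 × 2.56 / 1.0² = 53.8, so 54 per arm and 108 in total.

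Fixing one method in advance for each secondary outcome would be tidy but is optional.

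The exemption costs only wording. The small downside is that a mean-based result is somewhat more sensitive to outliers, which the bootstrap analysis would show.

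### Lactate non-inferiority is to be decided by comparing two separate group confidence intervals, with no margin and no interval for the difference, which is not the test the trial was sized for

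*Combined protocol and SAP*

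**What the plan says.** For lactate, the Statistical Analysis section calculates a 95% CI for the mean in each group and then states: "Comparison of the 95% CI in each group will then determine non-inferiority or inferiority". It does not say which relation between the two intervals counts as non-inferior, and no margin appears in the rule.

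The Sample size analysis section describes something else: "A total sample size of 98 patients will be needed to detect a non-inferiority margin of 30% with 90% power", by a one-sided two-sample t-test at alpha 0.025. The planning values are a mean of 3.5 and an SD of 1.6 mmol/L. The same section also sets the margin at a lactate value of 4.5.

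Three other statements in the Statistical Analysis section matter here:

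- Continuous variables are first checked with a Kolmogorov-Smirnov test, and "non-normally distributed variables will be analyzed with the Mann-Whitney U test". Lactate is not expressly exempted.
- On adjustment: "These analyses will be supplemented by multivariable logistic regressions to adjust for confounders". No linear model is named, and the confounders are not listed.
- Under "Additional interaction analyses for the primary outcome will be performed for the following subgroups", item 8 reads "Within oxygen group: Duration of oxygen exposure", split at 50% of active labor.

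**The concern.** A non-inferiority conclusion is a statement about the difference between arms relative to a margin. Two intervals computed separately do not give that statement unless the plan says how they are combined and where the margin enters. Because it says neither, the same data could be called non-inferior or not depending on a choice made after the results are seen, and the alpha and power in the sample size section do not carry over to the decision. This affects the trial's headline conclusion.

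Two smaller matters sit alongside. Lactate, the other cord-gas values and malondialdehyde are continuous, but the only adjusted model named is for binary outcomes. Item 8 exists in one arm only, so it cannot yield a treatment-by-subgroup interaction.

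**Working it through.** **Inputs.** From Sample size analysis: mean 3.5, SD 1.6, margin 30%, one-sided alpha 0.025, power 90%, totals of 98 and 114. From Strategy: 1:1 allocation. Results are given for 57 / 49 per arm (114 / 98 analysed).

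**Step 1: reproduce the plan's figure.** 30% of 3.5 is 1.05. Per arm, 2 × (1.960 + 1.282)² × (1.6/1.05)² = 48.8, so 49 and a total of 98, as stated. The trial was therefore sized on a difference in means.

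**Step 2: the matching rule.** The SE of the difference is 1.6 × √(2/n) = 0.300 / 0.323. The 95% CI half-width is 1.981 × 0.300 = 0.594 and 1.985 × 0.323 = 0.642. Non-inferiority at 1.05 needs an observed difference below 1.05 − 0.594 = 0.456, or 1.05 − 0.642 = 0.408. The error rate at a true difference of 1.05 is 2.5%. Power at no difference (noncentral t) is 93.5% / 89.5%.

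**Step 3: the rule as written, under four readings.** Each group CI has half-width t × 1.6/√n = 0.425 / 0.460. Error means declaring non-inferiority when room air is truly 1.05 worse.

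| Reading | Calculation | Error, 57 / 49 per arm |
|---|---|---|
| (i) The group CIs overlap | Satisfied up to an observed difference of 0.849 / 0.919; Φ((0.849 − 1.05)/0.300), Φ((0.919 − 1.05)/0.323) | 25% / 34% |
| (ii) Room-air upper limit below observed oxygen mean + 1.05 | Φ(−0.425/0.300), Φ(−0.460/0.323) | about 8% at both sizes |
| (iii) Room-air upper limit minus oxygen lower limit below 1.05 | Φ(−0.849/0.300), Φ(−0.919/0.323) | 0.2–0.3% |
| (iv) Room-air upper limit below 4.5, oxygen mean 3.5 | Φ((4.5 − 0.425 − 4.55)/0.212), Φ((4.5 − 0.460 − 4.55)/0.229) | 1.3–1.5% |

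Simulation of normal data agrees; where a range is shown, the lower end is the formula and the upper end the simulation.

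Reading (iii) is safe on error but costs power. At no true difference it is Φ((1.05 − 0.849)/0.300) = 75% and Φ((1.05 − 0.919)/0.323) = 66%.

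Reading (iv) ignores the control arm, so its error depends on the oxygen mean. With room air still 1.05 worse, it passes in 14% / 13% of trials if that mean is 3.25, and in 55% / 48% if it is 3.0. Both of these means are assumptions; the documents give only 3.5.

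**Step 4: the two margins.** 30% of 3.5 is 1.05, while 4.5 − 3.5 is 1.0. At 1.0 the Step 1 formula gives 53.8, so 54 per arm and 108 in total. Power at 1.0 (noncentral t) is about 91% with 114 analysed and 86% with 98.

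**Step 5: the lesser points.** No arithmetic is needed. A logistic model gives no estimate in mmol/L. A contrast confined to the oxygen arm has no room-air counterpart from which to form an interaction. For patients masked for nearly all remaining labor, the share of active labor on oxygen largely reflects when in labor randomisation occurred. That last remark does not apply to interrupted or crossed-over patients.

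**The case against.** The strongest reply on the decision rule is that, because the comparison is undefined, no single error rate can be pinned on the plan. That stands. A reader might infer from reading (i) that the trial has a 25–34% chance of a false non-inferiority claim. The documents do not say that overlap is the criterion, and readings (iii) and (iv) stay below 2.5% at the documents' own oxygen mean. The high figures under reading (iv) need an assumed lower oxygen mean, and if 4.5 is taken literally as the margin, a true room-air mean of 4.05 is not a failure at all. What remains is that the rule is undefined and does not match the powered test.

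The gap between 1.05 and 1.0 is only 0.05 mmol/L. The lactate paragraph is also most naturally read as overriding the Kolmogorov-Smirnov routing. Both are fair points, and one line of text settles each.

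On adjustment, the logistic sentence also follows the chi-squared and Fisher sentence. It suits the binary outcomes: persistent Category II tracing ("Odds ratios and 95% CI will be calculated for the secondary outcome of persistent Category II FHT"), cesarean delivery and the neonatal diagnoses. Adjustment is supplementary in a randomised trial. A reader might infer that lactate will be dichotomised, but nothing in the plan says so, and no loss of information should be charged to it on that account.

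Item 8 is openly labelled as within the oxygen group, and the plan claims no dose effect. Only its place in the list is wrong.

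**Conclusion.** The decision rule for the primary outcome is wrong as written and should be changed. It uses no margin and no interval for the difference, and it departs from the t-test on which 98 patients were calculated. At a true difference of 1.05 and an oxygen mean of 3.5, its error ranges from about 0.3% to 34% across reasonable readings, against 2.5% for the CI of the difference. The one reading that clearly protects against error while using both arms has 75% / 66% power in place of 93.5% / 89.5%. These figures assume normal data, SD 1.6 in both arms, and 57 / 49 per arm.

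The randomised comparison itself is not compromised: made on the difference in means, it is valid and adequately sized. The missing linear model and the placing of item 8 are minor.

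**What to change.** 1. State that lactate non-inferiority is judged on the upper limit of the 95% CI for the difference in means (room air minus oxygen) against one margin fixed in advance, whatever the Kolmogorov-Smirnov result.
2. In Sample size analysis, reconcile 1.05 with 1.0 and keep one. At 1.05 the sample size is unchanged. At 1.0, 90% power needs 108 analysable patients by the plan's formula, which the 114 cover only if losses are few.
3. Keep logistic regression for binary outcomes. For lactate, the other cord-gas values and malondialdehyde, add a supportive linear regression reporting the adjusted mean difference with its 95% CI. Name the covariates in advance, from items already collected and known before randomisation.
4. Move item 8 out of the interaction list and report it as an exploratory, non-randomised description within the oxygen arm. Assign exactly 50% to one of the two categories.

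The cost is SAP wording and minor programming. No new data are needed. The oxygen-duration contrast becomes descriptive only.

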Consent will be obtained at time of admission to Labor & Delivery. Randomization to either the oxygen group or room air group will be performed when the patient is in active labor (defined as regular contractions and  $\geq 6$  cm cervical dilation) and develops Category II FHT necessitating intrauterine resuscitation as determined by the care provider team (Figure 3). This will be performed via a computer-generated randomization sequence in a 1:1 ratio. Patients randomized to the oxygen group will receive the above stated current management of oxygen via nonrebreather face mask at 10L/min and “per-protocol” defined as receiving the mask for at least 90% of the remaining duration of labor including during cesarean delivery. Patients randomized to the room air group will not receive oxygen for Category II FHT unless otherwise required for maternal indications. Alternative and/or additional intrauterine resuscitation techniques for both groups (i.e. fluid bolus, maternal repositioning, and discontinuation of oxytocin) will be left to

the discretion of the medical team. The initial 6 patients consented and randomized will be part of a compliance run-in with the same protocol as above.

[figure not shown]

Figure 3: Flow diagram for randomization and treatment groups  
 L&D: Labor and Delivery FHT: fetal heart tracing

Specific Aim 1: Determine the effect of maternal oxygen administration for Category II FHT on neonatal cord gas parameters

After delivery of the infant, a segment of the umbilical cord will be removed with immediate collection of umbilical artery and vein samples by trained providers. These samples will be sent to the hospital laboratory for routine cord gas measurements as is universally practiced on our Labor and Delivery unit.

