## **Data Collection**

The patient's primary nurse will perform real-time documentation of oxygen initiation, any disruption in intervention, administration of amnioinfusion and additional resuscitation techniques performed (number of times patient is repositioned, total intravenous fluids, discontinuation of oxytocin). Study staff will collect data from medical records on:

- 1) Antepartum history:
  - a. Demographic data: Maternal age, race
  - b. Obstetric history: parity, prior cesarean, gestational age at delivery
  - c. Medical history: BMI at initial prenatal visit, diabetes, chronic hypertension, severe anemia (Hemoglobin <7), tobacco use, illicit drug use
  - d. Prenatal course: diagnosis of hypertensive disorders, gestational diabetes, abruption, intrauterine growth restriction, oligohydramnios
- 2) Intrapartum data:
  - a. Indication for admission/induction
  - b. Oxytocin (duration, total received dose)
  - c. Analgesia
  - d. Duration of labor (first and second stage)
  - e. Diagnosis of chorioamnionitis
  - f. Mode of delivery
  - g. Indication for cesarean
  - h. Electronic fetal monitoring
- 3) Neonatal course:
  - a. APGARs
  - b. Neonatal weight

- c. Admission to special care nursery (SCN) or neonatal intensive care unit (NICU)
- d. Duration of admission to SCN or NICU
- e. Diagnosis of any of the following: hypoxic ischemic encephalopathy, respiratory distress syndrome, oxygen requirement, requirement of hypothermia therapy, seizures, sepsis or suspected sepsis, neonatal death

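### Adjustment for confounders is not limited to covariates fixed before randomization, and the lactate comparison uses none of the baseline predictors already recorded

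*Combined protocol and SAP*

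**What the plan says.** The Statistical Analysis section plans two populations: "Intention-to-treat (primary analysis) and per protocol analyses will be performed". For continuous outcomes, "Normally distributed variables will be compared using Student's t-tests and non-normally distributed variables will be analyzed with the Mann-Whitney U test". It then says that the tests are to be "supplemented by multivariable logistic regressions to adjust for confounders". No covariate is named, no selection rule is given, and nothing says when a covariate must have been measured.

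For the primary outcome, "95% confidence intervals (CI) will be calculated for the mean cord lactate levels in each group", and non-inferiority is judged by comparing those intervals. No covariate enters. Hypertensive disorders, diabetes, growth restriction and the tracing features seen before the intervention appear for lactate only as interaction subgroups.

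On timing, the Strategy section says randomization "will be performed when the patient is in active labor", at 6 cm or more, once Category II tracing calls for resuscitation. The intrapartum part of the Data Collection section includes the entries "Oxytocin (duration, total received dose" and "Duration of labor (first and second stage", together with chorioamnionitis and mode of delivery. The nurse also records repositioning, fluids, amnioinfusion and stopping of oxytocin. None of these is split at randomization.

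**The concern.** In a 1:1 randomized comparison, variables fixed before randomization differ between arms only by chance. Adjusting for them is optional and serves precision. Variables that arise afterwards are different, because treatment may have changed them. Conditioning on one removes whatever part of the effect runs through it, and can introduce bias if it shares unmeasured causes with the outcome.

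The plan leaves this open where it matters. Secondary Aim 1 studies mode of delivery as a possible effect of oxygen, yet nothing stops it from also serving as a confounder. The Strategy section leaves the other resuscitation techniques to the team's discretion in both arms, so they can respond to assignment. The outcomes most exposed are the binary ones that logistic regression fits: persistent Category II tracing and cesarean.

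The second half is an opportunity. Useful predictors are already collected, and a linear model could use them to narrow the interval for the lactate difference.

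**Working it through.** **1. The plan's own sample size.** Inputs from the Sample size analysis section: mean 3.5, SD 1.6 mmol/L, margin 30%, one-sided alpha 0.025, power 90%, no covariates. Margin = 0.30 × 3.5 = 1.05.

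n per arm = 2 × SD² × (1.960 + 1.282)² / margin² = 2 × 1.6² × 3.2415² / 1.05² = 48.8, so 49 per arm and 98 in total. This matches the plan. With the noncentral t distribution, power at 49 per arm is 89.5%. At 57 per arm (the planned 114 / 2) it is 93.5%.

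**2. What baseline covariates could add.** The documents give no R-squared for lactate, so it is assumed over a range. Residual SD = 1.6 × √(1 − R²); SE = residual SD × √(2/n); power is from the noncentral t with noncentrality 1.05 / SE.

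| Assumed R² | Residual SD | Power, 49 per arm | Power, 57 per arm |
|---|---|---|---|
| 0 | 1.60 | 89.5% | 93.5% |
| 5% | 1.56 | 91.0% | 94.6% |
| 10% | 1.52 | 92.4% | 95.6% |
| 20% | 1.43 | 94.9% | 97.3% |

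At 49 per arm the half-width of the 95% CI for the difference (1.96 × SE) falls from 0.63 to 0.62, 0.60 and 0.57 mmol/L. The degrees of freedom are left at 2n − 2; the few lost to covariates make little difference.

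**3. What adjusting for a consequence of treatment could do.** All inputs here are assumptions. Persistent Category II is 50% on oxygen. A post-randomization variable is present in 30% on oxygen and in 50% or 60% on room air. The direct effect of room air is 0.4 in log-odds, so the odds ratio adjusted for the variable is exp(0.4) = 1.49. The variable's own log-odds effect on persistence is +1.0 (harmful) or −1.0 (helpful).

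- *Harmful.* On oxygen, persistence is 42.7% without and 67.0% with the variable (0.7 × 0.427 + 0.3 × 0.670 = 0.50). On room air it is 52.7% and 75.2%. At 50% prevalence, 0.5 × 0.527 + 0.5 × 0.752 = 0.639, total OR 1.77. At 60%, 0.662, total OR 1.95. Adjustment shrinks both to 1.49.
- *Helpful.* On oxygen, 57.3% and 33.0%. On room air, 66.7% and 42.4%. At 50% prevalence, 0.5 × 0.667 + 0.5 × 0.424 = 0.545, total OR 1.20. At 60%, 0.521, total OR 1.09. Adjustment raises both to 1.49.

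As a check, if the variable is equally common in both arms (30%), the total OR is 1.46 in either case. The ordinary gap between marginal and conditional odds ratios therefore explains only 0.03 of these shifts.

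**4. Reach into the primary decision.** Lactate is continuous, its decision rule uses unadjusted intervals, and the adjusted models are logistic and supplementary. The effect on that decision is nil.

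**The case against.** The strongest reply is that the plan is already sound where it counts. The unadjusted intention-to-treat comparison is primary and valid, the sample size reproduces without covariates, and with all 114 analysed the power is 93.5%. All of that stands, which is why the missing lactate covariates are only a lost gain. It is also true that the word confounders is not misplaced throughout: the per-protocol analysis (mask worn for at least 90% of remaining labor) and the within-oxygen comparison by duration of exposure are not randomized comparisons, and confounding is a proper concern there.

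A reader might infer four stronger things that the documents do not support.

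- *That covariates will be chosen by imbalance, or from the Data Collection list.* The Statistical Analysis section states no selection rule and does not refer to that list.
- *That the list is largely post-randomization.* Counting 43 items, about 17 precede randomization, 18 clearly follow it, 7 straddle it, and neonatal weight is measured later but essentially fixed before. Post plus straddling is 25 of 43 (58%). Without the neonatal items it is 15 of 32 (47%). Some classifications are judgement.
- *That adjustment pulls toward no difference.* Step 3 shows that it can go either way. Fluids, repositioning and stopping oxytocin are meant to help the fetus, so the helpful case is at least as plausible for them.
- *That false non-inferiority on lactate is at risk.* This would need a lactate model adjusted for post-randomization variables, which the plan does not contain.

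**Conclusion.** The point holds in a limited form. The supplementary adjusted analyses of randomized comparisons do not exclude variables that treatment can change, so their odds ratios for persistent Category II tracing and cesarean could be biased in an unknown direction. The sizes in step 3 are illustrations resting on assumed effects. The primary lactate conclusion is not affected.

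The absence of baseline covariates from the lactate comparison is a missed gain in precision: 1.5 to 5.4 percentage points of power at 49 per arm, or 1.1 to 3.8 at 57 per arm, for an assumed R-squared of 5% to 20%. These figures refer to the two-sample test behind the sample size with the 1.05 margin, not to a comparison of two separate group intervals. If the margin is read instead from the 4.5 cut-off in the same section (4.5 − 3.5 = 1.0), unadjusted power is 86.5% at 49 and 91.1% at 57 per arm.

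**What to change.** - **Lactate.** Estimate the between-arm difference and its 95% CI from a linear model with a short covariate set named before outcome data are seen, for example recurrent late, recurrent variable or prolonged decelerations before the intervention, growth restriction and parity. Report the unadjusted difference beside it.
- **Supplementary intention-to-treat logistic models.** Use only covariates fixed before randomization, and fewer of them where events are few. State that oxytocin totals, labor duration, mode of delivery, chorioamnionitis diagnosed after randomization and resuscitation measures are not adjusted for.
- **Per-protocol and within-oxygen duration analyses.** Keep confounder adjustment here, and say that these are not randomized comparisons.

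The cost is SAP wording. The example covariates are already recorded or will be read from the tracing. The five named would use 5 of the 112 residual degrees of freedom available with 114 patients (114 − 2), leaving 107.
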